- In Section 5, Table 5 (Table of Events, formerly Table 3), the abdominal examination for the abdominal mass assessment was removed from the table since it had caused some confusion. Even though removed, the abdominal examination for the abdominal mass assessment is performed at each visit when the CDAI [REDACTED] assessments are required. Therefore, in Section 5, Table 5 (Table of Events) Footnote d and Section 6.5.1 (Physical Examination), text was revised to emphasize that an abdominal examination will be performed at every visit (including those visits at which a complete or partial physical examination is not being performed) to assess the presence of an abdominal mass for the CDAI, [REDACTED] and PCDAI calculations.
- In Section 6.4.2 (Lost to Follow-up), some of the content was changed to provide more flexibility on how and how many times a site may contact a subject if lost to follow-up. This language is consistent now with all the Phase 3 GED-0301 studies.
- In Section 6.6.1 (Screening Visit), the text in the two sub-bullets “prior concomitant medications evaluation” and “adverse event evaluation” were revised to emphasize that ongoing concomitant medications and ongoing AEs from the core GED-0301 study will be electronically carried forward and do not need to be recorded in the appropriate eCRFs for this study.
- In Section 6.6.2 (Crohn’s Disease Activity Index), some of the content was corrected or updated to emphasize that clinical parameters needed for calculation of the CDAI will be collected by the subject via an electronic diary device and by the site at the scheduled visit via a separate electronic device. Also, under the list of categories the subject has experienced within the past 7 days, erythema nodosum and pyoderma gangrenosum were switched to the category with aphthous ulcers (previously in the same category with iritis/uveitis).

- [REDACTED]

- [REDACTED]

- In Section 7.1 (Description of Investigational Products) and Protocol Summary (Study Treatments), the text in the first sentence was updated to emphasize that GED-0301 will be provided as 40-mg “gastro-resistant, delayed release, pH-dependent” tablets and are not regular “coated” tablets.
- In Section 7.2 (Treatment Administration and Schedule), the title names of Tables 4 to 7 (Investigational Product Dispensing Schedule for the Treatment Periods at Year 1, Year 2, Year 3, and Year 4, respectively) were changed to better define the intended purpose, which is to identify visits when IP dispensing occurs, not when dosing occurs.
- In Section 7.2.2 (Overdose), the timeframe for overdose as previously defined was revised to be within the same calendar day and no longer within a 24-hour period.
- In Section 7.3 (Method of Treatment Assignment), the table numbers were updated from Table 4 to Tables 7 to 10.
- In Section 7.4 (Packaging and Labeling), the text was corrected to state that blister cards with child-resistant seals are used in this study and not opaque high-density polyethylene bottles with child-resistant caps.
- In Section 17 (References), the following references were added based on the addition of new information or assessments related to the addition of the adolescent population content within the protocol: [REDACTED]; Daperno, 2004; [REDACTED]; Griffiths, 1999; Hyams, 1991; Kansal, 2013; Kelsen, 2008; Lewis, 1997; Mamula, 2003; Markowitz, 2009; [REDACTED]; Pigneur, 2010; Ruemmele, 2014; [REDACTED]; [REDACTED]; Van Limbergen, 2008; [REDACTED]
- In Section 18 (Appendices), Appendix A (Table of Abbreviations) was updated with the removal of 4 abbreviations (ie, AS ODN, CpG, DNA and RNase) since text within the protocol was updated and these abbreviations are no longer applicable. The abbreviation DMC was added since Section 9.9.2 (External Safety Monitoring: Role of the Independent DMC) within the protocol was added. Also, other abbreviations were added based on the addition of the new pediatric and adolescent information.

1. LIST OF ABBREVIATIONS

Table 1: Abbreviations and Specialist Terms

Abbreviation	Meaning
AE	Adverse event
ALT	Alternating
APTT	Activated partial thromboplastin time
ATC	Anatomical Therapeutic Chemical
ATC2	Anatomical Therapeutic Chemical: Therapeutic (Level 2)
BMI	Body mass index
BUN	Blood urea nitrogen
CBC	Complete blood count
CD	Crohn's Disease
CDAI	Crohn's Disease Activity Index
CIC	Clinical Improvement Criteria
DAO	Data as observed
EAIR	Exposure-adjusted incidence rate
ECG	Electrocardiograms
ET	Early Termination
IP	Investigational product
IRTS	Interactive response technology system

Abbreviation	Meaning
LDH	Lactic dehydrogenase
LOCF	Last observation carried forward
MCH	Mean corpuscular hemoglobin
MCHC	Mean corpuscular hemoglobin concentration
MCV	Mean corpuscular volume
MedDRA	Medical Dictionary for Regulatory Activities
NRI	Nonresponder imputation
PBO	Placebo
PT	Preferred term
Q1	25 th percentile
Q3	75 th percentile
QD	Once Daily
RBC	Red blood cell
SAP	Statistical analysis plan
SD	Standard deviation
SES-CD	Simple Endoscopic Score for Crohn's Disease
SGOT	Serum glutamic-oxaloacetic transaminase
SGPT	Serum glutamic-pyruvic transaminase
SOC	System organ class
TEAE	Treatment-emergent adverse event
ULN	Upper limit of normal
VAS	Visual analog scale
WBC	White blood cell
WHODD	World Health Organization Drug Dictionary

2. INTRODUCTION

This statistical analysis plan (SAP) describes the analyses and data presentations for Celgene's protocol GED-0301-CD-004 "A Phase 3, Long-term Active Treatment Extension Study of Mongersen (GED-0301) in Subjects with Crohn's Disease" as amended on 06 Jan 2017. It contains definitions of analysis populations, derived variables and statistical methods for the analysis of efficacy and safety.

The study was terminated early by Celgene following an October 2017 recommendation of the Data Monitoring Committee. As such, changes are made to some protocol-specified analyses; these changes are described in relevant sections and summarized in Section 16.

In this SAP, GED-0301 160 mg once daily (QD), GED-0301 40 mg QD, and placebo QD are referred to as GED 160, GED 40, and PBO, respectively. Subjects will be assigned to receive one of 5 GED-0301 treatment regimens during the study, based on the treatment received during the core GED-0301 Phase 3 study (GED-0301-CD-002), and whether the subject met the clinical improvement criteria. For the first 12 weeks of the study, subjects will receive blinded, active GED-0301 treatment as one of the following numbered treatment groups:

- 1) continuous GED 160 for 12 weeks;
- 2) GED 160 for 4 weeks, PBO for 4 weeks, GED 160 for 4 weeks;
- 3) PBO for 4 weeks, GED 160 for 4 weeks, PBO for 4 weeks;
- 4) continuous GED 40 for 12 weeks;
- 5) PBO for 4 weeks, GED 40 for 4 weeks, PBO for 4 weeks.

Beginning at Week 12 through Week 208, subjects from the above-numbered treatment groups will continue to receive blinded, active GED-0301 treatment for 196 weeks as the following:

- 1) alternating PBO for 4 weeks and GED 160 for 4 weeks, through Week 208;
- 2) alternating PBO for 4 weeks and GED 160 for 4 weeks, through Week 208;
- 3) alternating GED 160 for 4 weeks and PBO for 4 weeks, through Week 208;
- 4) continuous GED 40, through Week 208;
- 5) alternating GED 40 for 4 weeks and PBO for 4 weeks, through Week 208.

The treatment regimens of alternating GED 160 for 4 weeks and PBO for 4 weeks (irrespective of whether GED 160 or PBO is administered first in this extension study), continuous GED 40, alternating GED 40 for 4 weeks and PBO for 4 weeks, are referred to as GED 160 ALT, GED 40, and GED 40 ALT, respectively. Investigational product (IP) refers to GED 160, GED 40, or PBO.

4. INVESTIGATIONAL PLAN

4.1. Overall Study Design and Plan

To streamline this SAP, the Study Design section of the protocol is copied below, with the understanding that the references to Study GED-0301-CD-003 are no longer applicable since the study was not initiated before the study termination.

This is a Phase 3, double-blind, long-term active treatment extension study to evaluate the long-term safety [REDACTED] of GED-0301 for 208 weeks in adult and adolescent subjects with CD who previously participated in either of the following two Phase 3 GED-0301 studies:

- Study GED-0301-CD-002 (Adult Subjects)
- Study GED-0301-CD-003 (Adult and Adolescent Subjects)

The purpose of this study is to assess long-term safety data of GED-0301 for a period of up to 208 weeks in adult subjects (ie, ≥ 18 years of age) who participated in the core Phase 3 GED-0301-CD-002 and GED-0301-CD-003 studies and adolescent subjects (ie, 12 to 17 years of age) who participated in the core Phase 3 GED-0301-CD-003 study.

Although all subjects will receive active treatment, this study is double-blinded for the entire 208 weeks for the purpose of preserving the blind of the subject's treatment allocation in the initial, core Phase 3 GED-0301 study.

Subjects from Study GED-0301-CD-002 who completed the study at Week 52, or who met the early escape criteria (Appendix H of the protocol) and were discontinued during the time period beginning at Week 12 through Week 52, may be eligible to enter this study.

Subjects from Study GED-0301-CD-003 who completed the study at Week 12 may also be eligible to enter this long-term active treatment study.

Subjects who discontinued Studies GED-0301-CD-002 or GED-0301-CD-003 prior to the Week 12 Visit are not eligible for this study.

This long-term active treatment study will consist of 3 periods:

- Screening Period – up to 4 weeks (ie, 1 day to 28 days depending on when long-term active treatment is available for the subject at the study center)
- Long-term Active Treatment Period – 208 Weeks (Week 0 to Week 208)
- Follow-up Period – 4 weeks (ie, no IP taken)

At Week 12, subjects will be evaluated to determine if they should be discontinued from the study based on clinical criteria. Subjects, who meet the following criteria, will be discontinued from the study at Week 12:

Subjects who complete this study through Week 208 will have a 4-week Follow-up Visit. Subjects who prematurely discontinue treatment from the study at any time prior to Week 208 will have an ET Visit and a 4-week Follow-up Visit. The ET Visit should be scheduled as soon as possible after the last dose of IP. If the ET Visit occurs 28 days after the last dose of IP, then the Follow-up Visit is not required.

At the Screening Visit in this study, all subjects who meet the inclusion criteria and do not meet the exclusion criteria will be eligible and assigned a subject identification number using a centralized interactive response technology system (IRTS).

Once the subject is eligible and registered in the IRTS, the assigned treatment is based on the clinical improvement criteria from the core GED-0301 study to determine the subject's course of treatment for the entire 208 weeks in this study.

Please note that all 160 mg once daily treatments are taken as four 40 mg tablets once daily in this study. That is, GED-0301-treated subjects who received one 160 mg tablet QD in GED-0301-CD-003 will receive four 40 mg tablets QD in this study.

Subjects will receive the following treatments:

Previously-treated GED-0301 subjects in Study GED-0301-CD-002 who met the clinical improvement criteria at Week 52:

- Will continue to receive their same blinded treatment, which will be:
 - Alternating PBO QD for 4 weeks and GED-0301 40 mg QD for 4 weeks, or
 - Continuous GED-0301 40 mg QD, or
 - Alternating PBO QD for 4 weeks and GED-0301 160 mg QD for 4 weeks.

Previously-treated GED-0301 subjects in Study GED-0301-CD-003 who met the clinical improvement criteria at Week 12:

- Will receive blinded treatment with:
 - Alternating PBO QD for 4 weeks and GED-0301 160 mg QD for 4 weeks.

Previously-treated PBO subjects who met the clinical improvement criteria:

[figure not shown]
- At Week 52 in Study GED-0301-CD-002; or
- At Week 12 in Study GED-0301-CD-003
- Will receive blinded treatment with:
 - Alternating GED-0301 160 mg QD for 4 weeks and PBO QD for 4 weeks.

Previously-treated GED-0301 or PBO subjects who did not meet the clinical improvement criteria:

- At Week 12 through Week 52 in Study GED-0301-CD-002; or
- At Week 12 in Study GED-0301-CD-003
- Will receive blinded treatment with:
 - Alternating GED-0301 160 mg QD for 4 weeks and PBO QD for 4 weeks, if the subject previously received GED-0301 treatment, or
 - GED-0301 160 mg QD for 12 weeks, if the subject previously received PBO, and after Week 12, subjects will receive alternating PBO QD for 4 weeks and GED-0301 160 mg QD for 4 weeks.

See the overall study design (Figure 1) for an overview of the study blinded-active treatments. All subjects will receive a blinded-active GED-0301 treatment regimen for 208 weeks, and the full descriptions of the treatment assignments are detailed in Appendix G of the protocol.

Figure 1 Overall Study Design

[REDACTED]

[REDACTED]

[REDACTED]	[REDACTED]	[REDACTED]	[REDACTED]
[REDACTED]	[REDACTED]	[REDACTED]	[REDACTED]
		[REDACTED]	[REDACTED]
[REDACTED]	[REDACTED]	[REDACTED]	[REDACTED]
		[REDACTED]	[REDACTED]
[REDACTED]	[REDACTED]	[REDACTED]	[REDACTED]

[REDACTED]

4.3. Stratification, Randomization, and Blinding

There is no randomization or stratification in this study. Eligible subjects will be assigned via an IRTS to receive one of 5 double-blind GED-0301 treatment regimens (Section 2) during the study, based on the treatment received during the initial, core GED-0301 Phase 3 study, and whether the subject met the clinical improvement criteria.

4.4. Sample Size Determination and Power Considerations

No sample size and power calculations are performed for this long-term active treatment study.

5. GENERAL STATISTICAL CONSIDERATIONS

5.1. Treatment Grouping Approaches

In listings, treatment will be displayed in 5 treatment regimens (corresponding to the 5 numbered treatment groups in Section 2), as follows:

- GED 160 12WK/PBO/GED 160 ALT
- GED 160/PBO ALT
- PBO/GED 160 ALT
- GED 40
- PBO/GED 40 ALT

The following treatment grouping will be used in tables.

- GED 40 ALT
- GED 40
- GED 160 ALT (combining all variants of this regimen)
- GED Total

5.2. Reporting Conventions

The following reporting conventions apply generally to tables, listings, and figures:

- P-values will not be reported.
- Confidence intervals (CIs) will be presented as 2-sided 95% CIs.
- Summary statistics will consist of the number and percentage of subjects in each category for discrete variables, and the sample size, mean, standard deviation (SD), median, minimum, 25th percentile (Q1), 75th percentile (Q3), and maximum for continuous variables.
- [REDACTED]
- [REDACTED]
- Change from baseline is calculated as the post-baseline value minus the baseline value. Percent change from baseline is calculated as $100 \times (\text{change from baseline} / \text{baseline})$. To assess change from baseline, a baseline value and at least 1 post-baseline value are required.

CEL GENE PROPRIETARY INFORMATION

6. SUBJECT DISPOSITION

The number of subjects screened, the numbers and percentages of subjects enrolled and not enrolled, and the numbers and percentages of the eligibility criteria failed will be summarized based on all subjects screened.

The number and percentage of subjects included in the analysis population will be summarized based on all subjects enrolled.

Subject disposition (entered, completed, discontinued, along with the primary reason for discontinuation) will be summarized for

- Week 12 (based on all subjects enrolled)
- Long-term Active Treatment Period (based on all subjects enrolled)
- Follow-up Period (based on all subjects who enter the Follow-up Period).

A listing of discontinued subjects with reason for discontinuation will be provided.

The number and percentage of subjects by region, country, and site will be provided based on all subjects enrolled.

7. **PROTOCOL DEVIATIONS/VIOLATIONS**

Protocol violations and deviations will be summarized using the long-term active treatment population.

A listing of all protocol violations and deviations in the study will be provided.

CELGENE PROPRIETARY INFORMATION

8. DEMOGRAPHICS AND BASELINE CHARACTERISTICS

Demographics and baseline characteristics, as collected or calculated in the core GED-0301 Phase 3 study, will be summarized based on the long-term active treatment population. Subject data listings will be provided.

8.1. Demographics and Baseline Characteristics

The following characteristics will be summarized as continuous variables:

- Age (years)
- Baseline body weight (kg)
- Baseline body mass index ($BMI = \text{weight (kg)} / [\text{height(m)}]^2$; kg/m^2)

The following characteristics will be summarized as categorical variables:

- Age (< 65, ≥ 65 years; < 40, 40 – < 65, 65 – < 75, ≥ 75 years)
- Sex (Male, Female)
- Race (American Indian or Alaska Native, Asian, Black or African American, Native Hawaiian or Other Pacific Islander, White, Not Collected or Reported, Other)
- Ethnicity (Hispanic or Latino, not Hispanic or Latino, Unknown, Not Reported)
- Region (North America, Western Europe, Eastern Europe, Asia Pacific)
- Baseline body weight (< 55, 55 – < 70, 70 – < 85, 85 – < 100, ≥ 100 kg)
- Baseline BMI (< 18.5, 18.5 – < 25, 25 – < 30, 30 – < 35, 35 – < 40, and ≥ 40 kg/m^2)
- Alcoholic beverages (yes [< 1 drink per week, 1 – 14 drinks per week, > 14 drinks per week], no)
- Tobacco history (never smoked, past smoker, current smoker, passive smoker, smokeless tobacco user)

8.2. Baseline Disease Characteristics

The following baseline disease characteristics will be summarized as continuous variables:

- Baseline CDAI score
- Baseline SES-CD score (central read)

- Baseline CDAI score (≤ 300 , > 300 ; < 220 , $220 - < 270$, $270 - < 330$, $330 - < 390$, $390 - \leq 450$, > 450)
- Baseline SES-CD (central read; < 6 , $6 - 12$, > 12)

9. EXTENT OF EXPOSURE TO INVESTIGATIONAL PRODUCT

9.1. Treatment Duration

Treatment duration will be summarized for Weeks 0-208 using the long-term active treatment population.

Treatment duration will be summarized as a continuous variable, and as a categorical variable with the following exposure intervals:

- Weeks 0-208: ≤ 13 , $> 13 - \leq 26$, $> 26 - \leq 39$, $> 39 - \leq 52$, $> 52 - \leq 65$, $> 65 - \leq 78$, $> 78 - \leq 91$, $> 91 - \leq 104$, $> 104 - \leq 117$, $> 117 - \leq 130$, $> 130 - \leq 143$, $> 143 - \leq 156$, $> 156 - \leq 169$, $> 169 - \leq 182$, $> 182 - \leq 195$, > 195 weeks.

A subject data listing of study drug records will be provided.

9.2. Treatment Compliance

As part of the routine recording of the amount of IP taken by each subject, the numbers of tablets dispensed and returned will be recorded at each visit (except the screening and follow-up visits). These records will be used to calculate treatment compliance. Treatment compliance will be summarized for Weeks 0-208 using the long-term active treatment population.

Treatment compliance rate will be summarized as a continuous variable, and as a categorical variable with the following categories: $< 75\%$, $\geq 75\% - \leq 120\%$, and $> 120\%$.

A subject data listing of drug accountability records will be provided.

9.3. Overdose

A subject data listing of overdose records will be provided.

10. CONCOMITANT MEDICATIONS AND PROCEDURES

Concomitant medications and procedures during the Long-term Active Treatment Period will be summarized for Weeks 0-208 using the long-term active treatment population.

10.1. Concomitant Medications

[REDACTED]

Concomitant medications will be coded according to the ATC coding scheme of the WHODD, and summarized by ATC2 level and standardized medication name, with ATC2 levels and standardized medication names within each ATC2 level sorted in descending order of frequency.

10.2. Concomitant Procedures

Concomitant procedures are defined similarly to concomitant medications. Concomitant procedures will be coded according to the MedDRA, and summarized by SOC and PT, with SOCs sorted in alphabetical order and PTs within each SOC in descending order of frequency.

11. EFFICACY ANALYSIS

The efficacy endpoints will be summarized descriptively.

11.1. Missing Data Handling

Continuous endpoints by time point will be summarized based on data as observed (DAO), where only subjects with sufficient data at the time point under consideration will be included in the summary of that time point.

11.2. Analyses of Efficacy Endpoints

11.2.1. Primary Efficacy Endpoint

There is no primary efficacy endpoint in this study.

11.2.2. Analyses of Secondary Efficacy Endpoints

As Study GED-0301-CD-003, where adolescent subjects were to be enrolled, was not initiated before the early termination of this study, there are no secondary efficacy endpoints.

[REDACTED]

[REDACTED]

12. SAFETY ANALYSIS

Safety will be evaluated via descriptive statistics and point estimates. No inferential testing for statistical significance will be performed.

[REDACTED]

12.2. Adverse Events

Adverse events (AE) will be coded according to the MedDRA. Unless otherwise specified, AEs will be summarized by SOC and PT, with SOCs sorted in alphabetical order and PTs within each SOC in descending order of subject incidence of the GED Total group combining all GED-0301 treatment regimens.

For the analysis of AEs, the following point estimates are provided, unless otherwise specified:

- Subject incidence: Subject incidence (ie, percentage [%] used in a frequency summary) is defined as the number of subjects with the specific event divided by the number of subjects included in the analysis. Subjects with multiple occurrences of the specific event in the specific analysis period will be counted only once in the numerator.

- [REDACTED]

A subject data listing of all AEs (including treatment-emergent AEs [TEAEs] and non-TEAEs) will be provided.

12.2.1. Overall Summary of TEAEs

An overall summary of the following TEAE categories will be provided for Weeks 0-208:

- Any TEAE
- Any drug-related TEAE
- Any severe TEAE
- Any serious TEAE
- Any serious drug-related TEAE
- Any TEAE leading to drug interruption
- Any TEAE leading to drug withdrawal
- Any TEAE leading to death

12.2.2. All TEAEs

All TEAEs will be summarized by SOC and PT as well as by PT only (in descending order of subject incidence of the GED Total group combining all GED-0301 treatment regimens) for Weeks 0-208.

12.2.3. Drug-related TEAEs

Drug-related TEAEs will be summarized for Weeks 0-208.

12.2.4. TEAEs by Maximum Severity

All TEAEs will be summarized by maximum severity (mild, moderate, and severe) for Weeks 0-208. If a subject reports multiple occurrences of a specific event within a specific analysis period, the subject will be counted only once by the maximum severity. If the severity is missing for one or more of the occurrences, the maximum severity of the remaining occurrences will be used.

12.2.5. Serious TEAEs

Serious TEAEs will be summarized for Weeks 0-208.

A subject data listing of all serious AEs (both TEAEs and non-TEAEs) will be provided.

12.2.6. TEAEs Leading to Drug Withdrawal

TEAEs leading to drug withdrawal will be summarized for Weeks 0-208.

A subject data listing of AEs leading to drug withdrawal will be provided.

12.2.7. Deaths

A subject data listing of all deaths will be provided.

12.3. Clinical Laboratory Evaluations

The following protocol-specified parameters from the central laboratory will be summarized:

- Hematology panel will include: complete blood count (CBC) with differential, including red blood cell (RBC) count, hemoglobin, hematocrit, mean corpuscular hemoglobin (MCH), mean corpuscular hemoglobin concentration (MCHC), mean corpuscular volume (MCV), white blood cell (WBC) count (with differential), and platelet count.
- Serum chemistry panel will include: total protein, albumin, calcium, phosphorous, glucose, total cholesterol, triglycerides, uric acid, total bilirubin, alkaline phosphatase, aspartate aminotransferase (AST)/serum glutamic oxaloacetic transaminase (SGOT), alanine aminotransferase (ALT)/serum glutamic pyruvic transaminase (SGPT), sodium, potassium, magnesium, chloride, carbon dioxide, blood urea nitrogen (BUN), creatinine, and lactic dehydrogenase (LDH), .
- Coagulation assessment will include: prothrombin time and activated partial thromboplastin time (APTT)
- Complement activation factor panel will include: compliment activation factors Bb, C3a and C5a.
- Urinalysis will include specific gravity and pH.

Summary statistics of observed values and changes from baseline will be provided by time point (time points include the scheduled visits for labs, the follow-up visit, and the end of Weeks 0-208).

Frequency summaries (shift tables) of shifts from baseline to post-baseline time points (time points include the scheduled visits for labs, the end of Weeks 0-208, and the worst value of Weeks 0-208) by category of low/normal/high/both low and high (the last category for the shift to the worst value only) will be provided for hematology and serum chemistry.

A summary of laboratory marked abnormalities as defined in Section 18.1 will be provided for Weeks 0-208.

A separate summary of laboratory marked abnormalities will also be presented by normal baseline and abnormal baseline.

A subject data listing of all laboratory data (including urinalysis) will be provided.

[figure not shown]

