6.5.3. Clinical Laboratory Assessments

Clinical laboratory evaluations will be performed by a central laboratory to include the following laboratory assessments performed at the frequency specified in [Table 5](#) and [Table 6](#):

- Hematology panel will include: complete blood count (CBC) with differential, including red blood cell (RBC) count, hemoglobin, hematocrit, mean corpuscular hemoglobin (MCH), mean corpuscular hemoglobin concentration (MCHC), mean corpuscular volume (MCV), white blood cell (WBC) count (with differential), and platelet count.
- Chemistry serum panel will include: total protein, albumin, calcium, phosphorous, glucose, total cholesterol, triglycerides, uric acid, total bilirubin, alkaline phosphatase, aspartate aminotransferase (AST)/serum glutamic oxaloacetic transaminase (SGOT), alanine aminotransferase (ALT)/serum glutamic pyruvic transaminase (SGPT), sodium, potassium, magnesium, chloride, carbon dioxide, blood urea nitrogen (BUN), creatinine, and lactate dehydrogenase (LDH).
- Coagulation panel will include: prothrombin time (PT) and activated partial thromboplastin time (APTT).
- Complement activation factor panel will include: complement activation factors Bb, C3a and C5a.
- Urinalysis panel will include: specific gravity, pH, glucose, ketones, protein, blood, bilirubin, leukocyte esterase, nitrite, and urobilinogen. The urinalysis will be completed at the central laboratory, not locally at the site. Microscopic urinalysis (bacteria, casts, crystals, epithelial cells, RBC, and WBC) will be performed only if the dipstick urinalysis is abnormal.

Clinical laboratory evaluations are not required to be fasting. However, the site will record whether a clinical laboratory evaluation was fasting or nonfasting on the laboratory requisition form.

Note: “Abnormal, clinically significant” results, if not related to a medical condition or diagnosis, should be recorded as an AE on the AE eCRF.

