9.7. Safety Analysis

Safety will be assessed by clinical review of all relevant parameters including treatment-emergent adverse events (TEAEs), laboratory tests, vital signs, weight, and ECGs. No inferential testing for statistical significance will be performed.

Treatment-emergent adverse events will be classified using the MedDRA classification system. All TEAEs will be summarized by system organ class, preferred term, severity, and relationship to IP. The TEAEs leading to death or to discontinuation from treatment and serious TEAEs will also be tabulated. In the by-subject analysis, a subject having the same event more than once will be counted only once and by greatest severity.

Laboratory, vital signs, weight, and ECG data will be summarized descriptively by time point. In addition, shift tables showing the number of subjects with values low, normal, and high compared to the normal ranges at baseline versus postbaseline will be provided for laboratory tests.

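### SAP 12.3 summarizes only specific gravity and pH from the ten-item urinalysis panel, leaving eight items, including protein and blood, with no by-visit or shift summary in the visible plan

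*SAP*

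**What the plan says.** Protocol 6.5.3 defines what the central laboratory reports: "Urinalysis panel will include: specific gravity, pH, glucose, ketones, protein, blood, bilirubin, leukocyte esterase, nitrite, and urobilinogen". Microscopy is added only when the dipstick is abnormal.

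Protocol 9.7 states how laboratory data will be analyzed: "Laboratory, vital signs, weight, and ECG data will be summarized descriptively by time point". It adds shift tables of low, normal and high values, "compared to the normal ranges at baseline versus postbaseline will be provided for laboratory tests". Neither sentence sets urinalysis apart.

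SAP 12.3 opens its list with "The following protocol-specified parameters from the central laboratory will be summarized". For urine the list reads "Urinalysis will include specific gravity and pH". Shift tables "will be provided for hematology and serum chemistry". The section then plans two further outputs that bear on urine:

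- "A summary of laboratory marked abnormalities as defined in Section 18.1 will be provided for Weeks 0-208", with a second version split by normal and abnormal baseline.
- "A subject data listing of all laboratory data (including urinalysis) will be provided".

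**The concern.** Long-term safety is the primary objective. For the adults who make up this study it is also the only primary or secondary objective: the protocol gives adults no secondary objectives, and SAP 11.2.2 states that no secondary efficacy endpoints remain. The laboratory tables are thus part of the main analysis.

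The two urine items kept are the numeric ones, which fit a table of means and changes from baseline. The eight dropped are dipstick results, which need a frequency table. The restriction therefore removes urine protein and blood from the by-visit summaries. In my judgment these are the dipstick results a safety reader would look for first; the documents do not rank them.

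At stake is whether a reader of the tables can see how often dipstick abnormalities occurred on each regimen. The listing holds the data but gives no counts or percentages.

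**Working it through.** The plan gives no figure to reproduce, so the check compares the two documents and counts.

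**1. Panel by panel (entries as listed in Protocol 6.5.3 and SAP 12.3)**

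| Panel | Protocol | SAP |
|---|---|---|
| Hematology | 8 | 8 |
| Serum chemistry | 20 | 20 |
| Coagulation | 2 | 2 |
| Complement | 3 | 3 |
| Urinalysis | 10 | 2 |

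Four panels are carried over in full and only urinalysis is cut. The SAP line is therefore a stated restriction and cannot be read as shorthand for the whole panel.

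**2. Items without a by-visit summary.** 10 − 2 = 8, and 8/10 = 80%. They are protein, blood, glucose, ketones, bilirubin, leukocyte esterase, nitrite and urobilinogen.

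**3. Do the shift tables recover them?** No. SAP 12.3 names hematology and serum chemistry only.

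**4. Does the marked-abnormality table recover them?** This cannot be checked, because Section 18.1 is not in the available text. If it covers urine protein or blood, frequencies by regimen would exist for those items. As described, though, that table covers Weeks 0-208 as a whole, so it would not supply the summary by time point in Protocol 9.7.

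**5. Do the adverse event tables recover them?** In part. Protocol 6.5.3 and 10.3 send an abnormal result to the adverse event form when it is clinically significant, needs treatment or leads to discontinuation. Such results appear in the tables of SAP 12.2 as event terms. Results judged not clinically significant do not. Protocol 6.5.4 also keeps findings related to Crohn's disease off the form unless they are serious.

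**6. Planned volume.** Table 5 of the protocol (adults) marks urinalysis after baseline at Weeks 12, 24, 40, 52, 80, 104, 128, 156, 184 and 208, which is 10 visits, and at Follow-up, making 11. The Week 40 mark carries a footnote whose text is not shown.

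- Planned maximum per completer: 8 items × 11 visits = 88 results (8 × 10 = 80 on treatment, plus 8 at Follow-up).
- The study stopped early, so 88 is a ceiling. As an illustration, assume a subject stops between Weeks 52 and 80. Four treatment visits plus Early Termination and Follow-up give 8 × 6 = 48 results. If the Early Termination Visit falls 28 days after the last dose and replaces Follow-up, the count is 8 × 5 = 40.

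**7. Is the format available?** Yes. SAP 5.2 already defines number and percentage per category for discrete variables. SAP 12.5 already plans a categorical shift table for ECG interpretation, and SAP 12.3 already uses the worst value of Weeks 0-208 for hematology and chemistry.

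**The case against.** The strongest reply is that little safety information is lost. Every urinalysis result is listed. An abnormality that matters clinically should become an adverse event and be tabulated by system organ class, preferred term, severity and relationship. Creatinine and blood urea nitrogen stay in the by-visit and shift tables, so renal function is still summarized. The sponsor's safety team reviews abnormal laboratory findings, and the Data Monitoring Committee reviews unblinded safety data. Protocol 9.1 leaves details to the SAP, and low/normal/high categories fit most dipstick items poorly. Regimens were assigned by prior treatment and improvement status, without randomization, so a difference between them would be hard to interpret.

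Most of this stands, and it rules out several stronger readings that a reader might infer:

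- That the eight items appear in no table at all. Section 18.1 is unseen and may include some of them.
- That a urinary signal could be found only by reading listings. The adverse event route gives clinically significant findings a place in the tables.
- That renal safety goes unexamined. The retained chemistry tables show otherwise.
- That the reduction is an undeclared departure. Two of the three entries in SAP Section 16 are redacted, so it may be declared there.

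The reply does not dispose of the core point. Protocol 9.7 promised a descriptive summary by time point, and neither a listing nor a set of adverse event terms provides one. Poor fit to low/normal/high calls for different categories and does not justify omission. Non-random assignment limits every laboratory table in this study equally, and the others are still produced.

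**Conclusion.** The point holds as a reporting gap against Protocol 9.7. Eight of ten urinalysis items (80%) have no by-visit or shift summary in the visible SAP. What is missing is the frequency, by regimen, of dipstick abnormalities that investigators did not report as adverse events.

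This rests on two things: reading the SAP 12.3 list as the complete set of parameters to be summarized, which its opening line supports, and the visible text alone. If Section 18.1 defines marked abnormalities for urine protein and blood, the gap narrows to the by-time-point summary for those two items. The planned ceiling of 88 results per completer is not an expected yield, because the study was terminated early and the documents do not show that anyone reached Week 208.

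No sample size, power or error rate is involved. Priority is low to moderate.

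**What to change.** In SAP 12.3, extend the urinalysis entry to the categorical items, at least protein and blood, and add:

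- number and percentage per result category at each scheduled urinalysis visit, at Follow-up and at the end of Weeks 0-208;
- a shift from baseline to the worst value of Weeks 0-208, using the categories that the central laboratory reports.

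Both should use the table groups already in SAP 5.1 (GED 40 ALT, GED 40, GED 160 ALT, GED Total). If Section 18.1 already covers some of these items, a cross-reference in 12.3 should say which. If the restriction is kept, Section 16 should state it with a reason, unless a redacted entry already does.

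The cost is one or two extra descriptive tables and a change of SAP wording. The data are already collected and planned for the listing, so no new procedure or data transfer is needed.
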